## STUDY ENDPOINTS:

Primary Outcome Measure:

Change in mean completion time for Graded Wolf Motor Function Test (GWMFT) Secondary Outcome Measure:

Change in grip relaxation time (following a maximum voluntary contraction (MVC)) Time required for muscle electromyographic (EMG) signals to reduce to within 3 SD of pre-MVC EMG activity.

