### Outcome Measures:

Subjects will be tested at the Arms and Hands Lab at baseline and the end of each week during the titration phase. Thus, data will be collected prior to administration of any agent, after one week at the lowest dosage of up to 8 mg per day, after one week at the next dosage of up to 16 mg per day, and after one week at the highest dosage of up to 24 mg per day. Data from the 4 testing sessions will be used to assess the impact of cyproheptadine on stroke. All outcome measures will be collected during each testing session. Pill counts will be performed each week as well to gauge subject compliance.

**Fig. 6.** Depiction of the interface between the fingers and the device. The motor shaft rotates the U-piece coupled to the proximal phalanges of the fingers. For the spasticity experiments, the proximal and distal interphalangeal joints will be fixed in neutral with finger splints.

Three potential manifestations of motoneuronal hyperexcitability will be quantified: spasticity, excessive coactivation during voluntary contraction, and prolonged muscle relaxation time. Spasticity will be precisely measured using techniques we have successfully employed in the past in which all four fingers are coupled to a servomotor through a custom jig (Fig. 6). Rotation of the servomotor shaft produces equivalent rotation of the MCP joints. The servomotor will impose constantvelocity rotation of the MCP joints in order to stretch the long finger flexors. Fast MCP rotation (300°/s) will be applied to evoke a stretch reflex. Slow MCP rotation (10°/s) will be imposed to measure nominally passive resistance. Wrist orientation and position will be fixed with a fiberglass cast which is subsequently clamped to a table (Fig. 6). MCP angle, angular velocity, and torque are recorded for analysis of spasticity. EMG recordings will be obtained with surface

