Title: Altering Activation Patterns Post-stroke **NCT:** NCT02418949 **Date:** 6/4/2014

Analysis: Spasticity will be quantified using the MCP angular position and torque data from the trials of imposed MCP rotation [27, 66-68]. Namely, the nominally passive torque curve (recorded during the 10°/s trial) will be subtracted from the total torque curve (recorded during the 300°/s). Mean reflex torque will then be computed from the resulting signal by averaging across a 300-ms period beginning at the end of stretch. The EMG data, normalized by the values recorded during maximum contraction, will be used to confirm that a reflex occurred. The FDS signal must surpass a threshold of 5% of maximal contraction for classification as a spastic stretch reflex and subsequent evaluation. Coactivation during voluntary tasks will be computed from the ratio of normalized EDC/FDS for flexion and FDS/EDC for extension. Values closer to 0 indicate less coactivation. Relaxation time will be estimated as the elapsed time from cessation of the auditory tone to the FDS signal dropping below a threshold level equal to three standard deviations of the resting signal [34]. Active isometric flexion and extension torque will be found by subtracting the initial, passive torque from the peak torque recorded during the respective trials.

Statistical analyses will be employed to assess the effect of cyproheptadine on these outcome measures. We will perform repeated measures analysis of variance (rmANOVA) with the between-subject factor Drug (cyproheptadine, placebo) and the within-subject factor evaluation Session (pre-administration, week 1, week 2, week 3 - see Fig. 1). To test the first hypothesis, addressing efficacy in reducing hyperexcitability, the measures spastic reflex, FDS relaxation time, and coactivation ratio will be used as dependent variables in a MANOVA. Should evidence of a significant effect appear, i.e., a Wilk's lambda value < 0.05, we will perform subsequent post-hoc ANOVAs to test the effects on individual dependent variables. To examine the second hypothesis, regarding loss of strength, separate rmANOVAs will be conducted for extension and flexion strength. Similarly, as we wish to minimize Type II errors for these potentially negative outcomes, separate rmANOVAs will be run for ESS and BDI-II without correction. Normality of the residuals will be tested for these parametric tests and non-parametric tests will be run if normality assumptions are violated.

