We will have 50 subjects in each of our Drug groups (cyproheptadine/placebo) in accordance with the power analysis performed for the whole study (see *Aim 2: Analysis*). Thus, we will be able to detect an effect size of 0.22 with a power of 80% for an α of 0.05 (G*Power 3.0 software [69]). In our pilot study examining a single dose of cyproheptadine, we observed a much greater effect size of 0.60 for the reduction in relaxation time. Importantly, the targeted subject numbers will allow us to detect even moderate decreases in strength or increases in somnolence.

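### The Aim 1 repeated-measures ANOVA counts the drug-free session as an outcome, names no term that tests the drug, and adjusts for neither the pre-drug value nor FMA

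*SAP*

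**What the plan says.** The SAP's Analysis section specifies a repeated-measures ANOVA with Drug (cyproheptadine, placebo) between subjects and "the within-subject factor evaluation Session (pre-administration, week 1, week 2, week 3" as the repeated factor. The Protocol, under Outcome Measures, confirms what the first level is: "data will be collected prior to administration of any agent".

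Three hyperexcitability measures (reflex torque, relaxation time, coactivation) go into a MANOVA, followed by individual ANOVAs. Flexion and extension strength, ESS and BDI-II each get their own repeated-measures ANOVA. The side-effect scales are left uncorrected "as we wish to minimize Type II errors for these potentially negative outcomes". None of these sentences names the model term that tests the drug, and none names a covariate. The Protocol (Study Timelines; Study Design) stratifies randomisation by initial FMA score.

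The SAP's power paragraph, for 50 subjects per Drug group and α = 0.05, says "we will be able to detect an effect size of 0.22 with a power of 80" per cent. It then compares this with a single-dose pilot: "we observed a much greater effect size of 0.60 for the reduction in relaxation time". It gives no tested term, effect-size scale or between-session correlation. Among the Protocol's Study Endpoints, the secondary outcome begins "Change in grip relaxation time (following a maximum voluntary contraction (MVC".

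**The concern.** A session recorded before any capsule is taken cannot carry a drug effect. If the Drug main effect is the test, that session is averaged with the three dosed ones. The estimate is then diluted, and it is not the change in relaxation time that the Protocol names as an endpoint. If Drug × Session is the test, the pre-drug session is used legitimately, through within-subject change. The test then spreads over 3 degrees of freedom and still does not adjust for baseline.

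The two terms differ in sensitivity, and which one is better depends on the correlation between sessions. With no term named, a reader cannot tell what effect Aim 1 can detect, and the choice stays open until the data are in.

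Aim 1 does not carry the primary endpoint. It does carry the secondary endpoint and the strength and somnolence analyses, where the SAP itself wants few missed harms.

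**Working it through.** **Inputs from the documents.** 50 subjects per Drug group, α = 0.05 and 80% power (SAP, power paragraph). Four sessions, the first drug-free (SAP, Analysis; Protocol, Outcome Measures).

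**Assumptions, because the documents give none.** Equal correlation r between sessions (0.3 to 0.7 shown), SD of 1 at each session, complete data, two-sided tests. Power is from the noncentral F distribution with noncentrality λ.

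**Step 1. Reproduce 0.22.** For the Drug main effect over four sessions, λ = f² × 100 × 4/(1 + 3r) with 1 and 98 df. Power of 80% needs λ = 8.006. At r = 0.5, f = √(8.006 × 2.5/400) = 0.224. Conversely, f = 0.22 gives λ = 0.0484 × 400/2.5 = 7.744 and 78.7% power.

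For Drug × Session, λ = f² × 400/(1 − r) with 3 and 294 df. Power of 80% needs λ = 11.05. At r = 0, f = √(11.05/400) = 0.166, and it falls as r rises (0.118 at r = 0.5). So 0.22 fits the main effect and not the interaction.

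**Step 2. Dilution.** With two equal groups f = d/2, so 0.22 is a difference of 0.44 SD in the average over all four sessions. An effect d present only at weeks 1-3 has a four-session average of (0 + d + d + d)/4 = 0.75d. For d = 0.44 this is 0.33 SD.

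**Step 3. Power at d = 0.44 in weeks 1-3, r = 0.5.**
- Drug main effect, four sessions: λ = 25 × 0.33²/((1 + 3r)/4) = 2.7225/0.625 = 4.36; power 54%.
- Drug × Session: λ = 25 × 0.75 × 0.44²/(1 − r) = 3.63/0.5 = 7.26; power 60%.
- Unadjusted mean of weeks 1-3: λ = 25 × 0.44²/((1 + 2r)/3) = 4.84/0.667 = 7.26 with 1 and 98 df; power 76%.
- Baseline-adjusted mean of weeks 1-3: λ = 25 × 0.44²/((1 + 2r)/3 − r²) = 4.84/0.4167 = 11.62 with 1 and 97 df; power 92%.

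Relative to the main effect, dropping the drug-free session takes power from 54% to 76%, and baseline adjustment takes it to 92%. A simulation of 20,000 trials gave 53.7% for the main effect and 91.5% for the adjusted mean.

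**Step 4. Detectable difference at 80% power, equal effect at weeks 1-3 (SD).** Adjusted week 3 uses λ = 25d²/(1 − r²) with 1 and 97 df.

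| r | Drug main effect | Drug × Session | Adjusted mean, weeks 1-3 | Adjusted week 3 |
|---|---|---|---|---|
| 0.3 | 0.52 | 0.64 | 0.38 | 0.54 |
| 0.5 | 0.60 | 0.54 | 0.37 | 0.49 |
| 0.7 | 0.66 | 0.42 | 0.32 | 0.40 |

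The better of the two unadjusted terms changes between r = 0.3 and r = 0.5.

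**Step 5. Other effect patterns at r = 0.5 (week 3 effect needed, SD).**

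| Pattern over weeks 1, 2, 3 | Drug main effect | Drug × Session | Adjusted mean | Adjusted week 3 |
|---|---|---|---|---|
| 1, 1, 1 | 0.60 | 0.54 | 0.37 | 0.49 |
| 1/3, 2/3, 1 | 0.90 | 0.63 | 0.55 | 0.49 |
| 0, 0, 1 | 1.79 | 0.54 | 1.10 | 0.49 |

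**Step 6. Decaying correlation.** With a first-order autoregressive pattern (lag-1 correlation 0.5) and an equal effect of 0.44 SD, simulated power for main effect / interaction / adjusted mean was 63/43/84%.

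**The case against.** The strongest objection is that the adjusted average is not always the best test. Dosing is titrated weekly, so an effect that grows with dose is a natural alternative, and averaging in the lower-dose weeks is then a milder form of the same dilution. Step 5 bears this out. Adjusted week 3 beats the adjusted average for the graded pattern, and Drug × Session beats it clearly for an effect confined to week 3. A harm that emerges only at the last step could be missed more often with the average. This stands, and it rules out recommending the average without conditions.

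It does not remove the case for baseline adjustment. The adjusted average needed a smaller effect than the four-session main effect in every pattern run. A baseline-adjusted 3-df test of weeks 1-3 matched or beat Drug × Session to within 0.002 SD.

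A reader might infer three stronger things that the documents do not support:
- **That the analysis is biased or invalid.** Randomisation protects either term, and keeping baseline as a level is legitimate when Drug × Session is the test. The Protocol itself says that all four sessions feed the drug assessment.
- **That 0.22 could belong to any test.** A main effect over three dosed sessions at correlation 0.4 also gives about 0.22 (0.219), but the SAP plans four sessions, and the interaction does not fit. The attribution to the four-session main effect is still an inference. The SAP refers to an Aim 2 analysis for the study's power calculation, and that text is not among the supplied documents.
- **That these figures describe the hyperexcitability MANOVA.** They are for single outcomes: the strength, ESS and BDI-II analyses and the follow-up ANOVAs.

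**Conclusion.** The point holds as a matter of efficiency and specification. The SAP treats a drug-free session as an outcome, leaves the tested term unnamed, and uses neither the pre-drug value nor the stratification factor. Its 0.22 most plausibly describes a main effect that shrinks an equal weeks 1-3 effect by a quarter. At 0.44 SD and correlation 0.5, the cost is power of 54% (or 60% with Drug × Session) where 92% is available from the same data.

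The size rests on assumed correlations, complete data and an equal effect at weeks 1-3. Under graded or late effects the adjusted average loses ground to adjusted week 3, and under a week-3-only effect to Drug × Session as well. The gain from adding FMA cannot be quantified, because the documents give no correlation between FMA and these outcomes. The issue merits correction but does not touch the primary endpoint.

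**What to change.** For each univariate Aim 1 outcome (hyperexcitability measures, strength, ESS, BDI-II):
- Model weeks 1-3 as the outcomes with Drug, Session and Drug × Session. Enter the pre-drug value, its interaction with Session, and the FMA stratification variable as covariates.
- Pre-specify one baseline-adjusted drug contrast, either the weeks 1-3 average or week 3, and report the other as supporting. State the downside of the choice, using the Step 5 comparison.
- Apply the MANOVA to the same adjusted contrast.
- Restate the power paragraph for the chosen contrast, with its scale and assumed correlation. For an equal effect at correlations 0.3/0.5/0.7, the detectable differences are 0.38/0.37/0.32 SD for the average and 0.54/0.49/0.40 SD for week 3. Put the pilot 0.60 on that scale before comparing the two.

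For reflex torque the SAP sets an EMG condition: "The FDS signal must surpass a threshold of 5% of maximal contraction". Do not enter a below-threshold indicator from weeks 1-3 as a covariate. It is measured after dosing starts and may itself respond to the drug.

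The SAP also says that "non-parametric tests will be run if normality assumptions are violated". Permuting Drug within FMA strata on the same adjusted contrast would be one way to do this, but it is optional.

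The cost is SAP wording and one restated sensitivity figure. All the data are already collected, and no patients or visits are added.

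### The SAP's gate for the Aim 1 MANOVA puts the 0.05 cut-off on Wilks' lambda itself instead of on its p-value

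*SAP*

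**What the plan says.** The SAP's paragraph on statistical analyses sets up Drug (two levels) as a between-subject factor and Session (four levels, from pre-administration to week 3) as a within-subject factor. For the first Aim 1 hypothesis, "the measures spastic reflex, FDS relaxation time, and coactivation ratio will be used as dependent variables in a MANOVA". The step from this joint test to the individual measures is governed by one sentence: "Should evidence of a significant effect appear, i.e., a Wilk's lambda value < 0.05, we will perform subsequent post-hoc ANOVAs".

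No other sentence in the SAP or protocol restates this rule as a p-value. A 5% level appears only in the power statement: "Thus, we will be able to detect an effect size of 0.22 with a power of 80% for an α of 0.05". The other Aim 1 analyses do not pass through the gate: "separate rmANOVAs will be conducted for extension and flexion strength", and "separate rmANOVAs will be run for ESS and BDI-II without correction".

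**The concern.** The sentence offers lambda below 0.05 as the definition of a significant effect. Small values of lambda do favour an effect, but the value that corresponds to a 5% test depends on the number of outcomes and subjects. With a two-level factor and 100 subjects it lies much nearer 1 than 0.

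Two things follow. An analyst who applies the written rule would stop at the MANOVA even with overwhelming evidence and would not run the individual efficacy tests for the first Aim 1 hypothesis. An analyst who applies the probable intention would get a working gate but would depart from the written rule, so a reader could not confirm that the rule used was the one fixed in advance.

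Relaxation time, one of the three gated measures, is also the only secondary outcome under Study Endpoints in the protocol. The sentence also leaves open whether the Drug term or the Drug × Session term opens the gate.

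**Working it through.** **Inputs.** Three dependent variables, a two-level Drug factor and four sessions (SAP, statistical analyses paragraph). Group size: "We will have 50 subjects in each of our Drug groups", so N = 100. Alpha 0.05, 80% power and effect size 0.22 (SAP, power statement).

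**The plan's own figure.** The SAP gives no derived value for the lambda cut-off; its only Aim 1 power figure is the 0.22. Take the between-subject effect in a repeated-measures ANOVA with m = 4 sessions and an assumed between-session correlation of 0.5 (the SAP states none). The noncentrality is f²·N·m / (1 + (m − 1)ρ) = 0.0484 × 100 × 4 / 2.5 = 7.744. On (1, 98) df the power is 0.787, close to the stated 80% (exactly 80% needs f = 0.224). Power is 0.885 at ρ = 0.3 and 0.697 at ρ = 0.7. The statement is thus consistent with an ordinary 5% F test. It does not depend on the lambda rule.

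**Lambda at p = 0.05.** For two groups and p outcomes the relation is exact:

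F = [(1 − Λ)/Λ] × (99 − p)/p on (p, 99 − p) df.

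With p = 3, the 95% point of F(3, 96) is 2.699, so Λ = 1 / (1 + 3 × 2.699/96) = 0.922.

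**F at lambda = 0.05.** F = (0.95/0.05) × 96/3 = 19 × 32 = 608, for which p is about 2.7 × 10⁻⁶².

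**As a separation between groups.** With 50 per group, Hotelling's T² = 98(1 − Λ)/Λ = 25D², where D is the observed Mahalanobis distance in SD units.

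- Λ = 0.922: D = 0.575.
- Λ = 0.05: D = √(98 × 19/25) = √74.48 = 8.63.
- Ratio: 8.63/0.575 = 15.0.

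**Against the pilot effect.** The SAP reports that "we observed a much greater effect size of 0.60 for the reduction in relaxation time", without saying which effect-size metric is used. Read as a standardised difference, it is 0.60 SD; read as Cohen's f for two groups, it is 1.2 SD. Assume that only relaxation time moves, that the three outcomes are uncorrelated, and that there is one value per subject. The median lambda is then about 0.896 or 0.715. In 400,000 simulated trials at each value none fell below 0.05, nor did any at a true separation of 5 SD. An even chance of lambda below 0.05 needs a true separation of about 8.5 SD. If all three outcomes were independent and each differed by 2 SD, a test at p < 0.05 would have essentially 100% power, while the literal rule would have essentially none.

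**Other readings of the MANOVA.** The SAP does not say how Session enters, so the cut-off was recomputed for other layouts with N = 100:

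| Layout | Responses | Λ at p = 0.05 | F at Λ = 0.05 |
|---|---|---|---|
| Three outcomes | 3 | 0.922 | 608 |
| Flexion and extension coactivation kept apart | 4 | 0.906 | 19 × 95/4 = 451.25 |
| 3 outcomes × 3 session contrasts | 9 | 0.834 | 190 |
| 3 outcomes × 4 sessions | 12 | 0.795 | 137.75 |

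If fewer subjects have complete data (assumed equal groups, three outcomes), the cut-off is 0.903 with 80 subjects and 0.871 with 60. Repeated sessions could raise the multivariate separation. However, with a constant on-drug effect and equal correlation between sessions (both assumed), an even chance under the literal rule would need a correlation of about 0.996 for 0.60 SD or 0.98 for 1.2 SD.

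**The case against.** The strongest reply is that this is shorthand. The sentence speaks of a significant effect, the power statement uses a 5% alpha, and nearly any statistician would run the test at p < 0.05. On that reading the gate works, and no estimate, sample size, primary endpoint or safety analysis changes. This is right, and it limits the severity. It does not make the written threshold correct.

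The figure 0.922 is conditional: it assumes three responses, one value per subject and all 100 subjects analysed. The SAP leaves room to doubt each, since there are four sessions, coactivation is defined by two ratios, and a reflex is evaluated only if the FDS signal passes 5% of maximum. That also stands, so 0.922 should be read as one layout among several. None of the layouts comes near 0.05.

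The metric of the pilot effect is unknown and could be a within-subject change, so the two readings above are illustrations.

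Finally, the protocol gives no time point or analysis for its secondary outcome, and the Aim 2 analysis that the SAP mentions is not in the text available. It is therefore not shown that this gate governs the formal test of that outcome. The link is only that the same measure is gated here.

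**Conclusion.** The concern holds and is minor. As written, the rule places a p-value cut-off on a test statistic. For three outcomes and 50 v 50 the two differ by a factor of 15 in observed separation (0.575 SD against 8.63 SD). That comparison is exact for a single-value, two-group MANOVA with complete data. The simulation and session results rest on the stated assumptions about effect size and correlation. The conclusion does not depend on them, because every layout examined puts the 5% cut-off between about 0.80 and 0.94. The intended rule is very likely p < 0.05. The error reaches only the three gated Aim 1 measures. It does not touch the primary outcome (Graded Wolf Motor Function Test completion time) or the ungated strength, ESS and BDI-II analyses.

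**What to change.** In the SAP sentence that opens the post-hoc ANOVAs, replace the lambda criterion with: *p < 0.05 for the F test of Wilks' lambda*. A p-value criterion is correct under every layout above, whereas any fixed lambda would be right for only one.

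In the same sentence, and before unblinding, the sponsor should name the drug-related term that opens the gate, Drug or Drug × Session. No term is recommended here. The better choice depends on the between-session correlation, which the documents do not give, and on how the effect develops over the titration weeks.

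The cost is one phrase and one decision, with no change to data collection, sample size or patient procedures.

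### The SAP gives no significance level or adjustment for the ANOVAs that follow the Aim 1 MANOVA; at 5% each, with exactly one measure responding, the chance of a false claim on the other two is about 9%

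*SAP*

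**What the plan says.** The second paragraph of the SAP's Analysis section tests the first Aim 1 hypothesis as one family: "the measures spastic reflex, FDS relaxation time, and coactivation ratio will be used as dependent variables in a MANOVA". If the MANOVA shows an effect, "we will perform subsequent post-hoc ANOVAs to test the effects on individual dependent variables". The gate is written as the Wilks' lambda statistic itself falling below 0.05, not as its p-value.

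No level and no adjustment is given for the follow-up ANOVAs. The only explicit remark on correction concerns the tolerability scales: "separate rmANOVAs will be run for ESS and BDI-II without correction". The only alpha stands in the power paragraph, where the SAP says "we will be able to detect an effect size of 0.22 with a power of 80% for an α of 0.05". That paragraph also cites a pilot effect of 0.60 for relaxation time, in an unstated metric. The protocol adds no multiplicity rule.

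**The concern.** When no measure responds, the MANOVA has to reject falsely before any single-measure claim can be made, so such claims are held to 5%. When one measure does respond, the gate opens because of that measure, and it then gives the other two little or no protection. The SAP's own pilot makes this case plausible, since it points to an effect on relaxation time.

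Aim 1 is likely to be read measure by measure: the protocol (Outcome Measures) lists spasticity, coactivation and relaxation time as separate manifestations, and the SAP plans tests on each. At stake is a claim that the drug reduces spasticity or coactivation when only relaxation time changed. Because the level is not stated, the rule could also be chosen after the results are known.

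**Working it through.** **Inputs from the SAP.** "We will have 50 subjects in each of our Drug groups (cyproheptadine/placebo"), so N = 100; three measures; alpha 0.05; four sessions: "within-subject factor evaluation Session (pre-administration, week 1, week 2, week 3". **Assumed, because the SAP gives neither:** a correlation between sessions of 0.5, and a correlation between measures of 0 to 0.7.

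**1. Reproduce the design effect.** Take 0.22 as Cohen's f for the between-subject Drug effect with m = 4 sessions. The noncentrality is f²·N·m / (1 + (m−1)·0.5) = 0.0484 × 100 × 4 / 2.5 = 7.74 on 1 and 98 degrees of freedom. Power is 78.7%, and the effect detectable at 80% is f = 0.224, so the SAP's figure is reproduced. In SD units of the four-session mean this is d = 2 × 0.22 / √(2.5/4) = 0.44 / 0.79 ≈ 0.56. This power is for one ANOVA, not for the MANOVA gate.

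**2. Ceiling, with the gate always open and two true nulls at 0.05 each.** If independent, 1 − 0.95² = 9.75%. With correlation between the measures it is 9.5% at 0.3, 9.1% at 0.5, 8.4% at 0.7 and 7.0% at 0.9.

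**3. With the gate included.** A three-variable Hotelling T² test (the two-group MANOVA) at p < 0.05 is followed by each ANOVA at 0.05. One measure truly responds, with 50 v 50 and 200,000 simulated trials per cell. The chance of at least one false claim on the other two is:

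| Real effect (SD) | Corr. 0 | 0.3 | 0.5 | 0.7 |
|---|---|---|---|---|
| 0.35 | 6.5% | 6.7% | 7.0% | 7.3% |
| 0.56 (design) | 8.8% | 8.9% | 8.8% | 8.3% |
| 0.6 | 9.1% | 9.1% | 9.0% | 8.5% |
| 1.0 | 9.7% | 9.4% | 9.2% | 8.4% |

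At the design effect the gate opens in 63% of trials at correlation 0 and 82% at 0.5. The 0.6 SD row is an illustrative value and not the pilot's 0.60.

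**4. Other configurations.** With no responder, the gate holds any false claim to 5%. With two responders, one null is left and the rate is 4.8%-5.2%. With three responders, no false claim is possible.

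**5. Under closed testing or Holm.** With one responder at 0.6-1.0 SD and correlation 0-0.5, the false-claim rate falls to about 4%-5% under either. Power per truly responding measure at 0.6 SD:

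| Case | As planned | Closed | Holm, no gate | Holm after gate |
|---|---|---|---|---|
| One responder, corr. 0 | 68% | 66% | 71%-72% | 65% |
| One responder, corr. 0.5 | 79%-80% | 77% | 71%-72% | 69% |
| Two responders, corr. 0 | 82.6% | 73.6% | – | – |
| Two responders, corr. 0.5 | 83.2% | 77.6% | – | – |

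With one responder at 1.0 SD, power is 99% or more under the plan, closed testing and Holm alike.

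**6. The gate as written.** With three variables and N = 100, F = ((1 − Λ)/Λ) × 96/3. The 5% critical value is F(3, 96) = 2.70, so p = 0.05 corresponds to Λ = 1 / (1 + 2.70 × 3/96) ≈ 0.92. For Λ = 0.05, T² = 98 × 0.95/0.05 = 1,862. Since T² = 25·D² with 50 per group, D = √(1,862/25) ≈ 8.6 SD. Read literally, the gate would almost never open.

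**The case against.** A reader might infer that the SAP prescribes uncorrected 5% tests. It does not: it is silent, and the 5% is borrowed from the power statement. A reader might also take the remark on ESS and BDI-II as a promise of correction elsewhere, and so call the error rate twice what was intended. That remark is not a stated promise, and no family-wise rate for single measures is given. The power paragraph refers to an Aim 2 analysis section that is not in the available SAP text, so a general convention may be set there. All of this stands. What remains is an unspecified rule.

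The 9% belongs to one configuration. The protocol presents the three measures as manifestations of the same hyperexcitability, so several responding together is at least as relevant as one responding alone. In that case the plan's error rate is already nominal and closed testing costs more power. This stands too, and both cases are shown above.

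The model uses one drug test per measure, while the SAP plans Drug by four Sessions. The figures are therefore illustrative. Leaving the term open does not help the plan: if a Drug or a Drug-by-Session result could each count, four independent tests on two null measures would give 1 − 0.95⁴ = 18.5%.

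Lastly, the protocol's primary endpoint is GWMFT time. Of these three measures only relaxation time is a listed endpoint, and it is secondary. That limits the weight of the point but does not remove it.

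**Conclusion.** The concern holds in a limited form. The SAP leaves the level and adjustment of the follow-up ANOVAs open, and the MANOVA gate alone does not protect the remaining measures once one responds. If each ANOVA is run at 0.05 and exactly one measure responds, the chance of a false claim on the other two is about 9% at the design effect for correlations up to 0.5. It is about 8% at correlation 0.7, about 6%-7% for a weak effect of 0.35 SD, and at most about 9.75%. It does not exceed about 5% when none, two or all three respond.

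These are rates over all trials, and they rest on the assumed correlations and on one drug test per measure. The documents do not support a flat statement that the error is 9%-10%. The lambda threshold is a separate error of wording and needs correcting whichever follow-up rule is chosen. The whole point is a worthwhile tightening of Aim 1 and does not bear on the primary endpoint.

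**What to change.** In the SAP's Analysis section:

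- State the gate as a MANOVA p-value below 0.05, in place of a lambda value below 0.05.
- Complete it as a closed test. Claim an effect on a single measure only if the three-variable test, both two-variable tests that contain the measure, and its own test are all below 0.05.
- Name the model term (Drug or Drug by Session) that counts as the claim, and use the same term at every step.

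This needs SAP wording and three extra two-variable tests, with no new data or subjects. At 0.6 SD the loss of power per measure is about 2-3 points with one responder and about 6-9 points with two.

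Holm across the three measures is a simpler alternative. Compared with the plan at 0.6 SD, it ranges from a gain of about 3 points (no gate, correlation 0, one responder) to a loss of about 8-10 points. If Holm is chosen, the SAP should say whether the MANOVA gate still applies.
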